Breach of confidentiality: There is a potential risk of loss of confidentiality. Consistent with the Federal guidelines, all patients and guardians will be informed of the federally mandated reporting laws for child abuse and neglect, verbally and in the written consent form. Therefore, if abuse or neglect is suspected, per institutional and legal standards and requirements, the Department of Human Services may be called if appropriate and indicated. Risks associated with this reporting include embarrassment, legal consequences, and removal of the child from home.

3. Specific Aims and Hypothesis

Specific Aims	Hypothesis

SA1: Evaluate the safety of CIS-telehealth relative to inpatient and OCIC-in-person among children with similar CHRT-SR scores.
	
 Our working hypothesis is that CIS-telehealth is associated with a greater risk of suicidal event relative to inpatient and in-person OCIC. Response is defined by a delay in first recurrence of a suicidal event and a lower number of suicidal events over 90 days and 180 days. Clinical Features: 
 Severity of suicidal ideation at baseline and over 180 days number of suicidal events at baseline only Substance use at baseline and over 180 days. Sociodemographic features: Age, Gender, Gender Identity, Type of insurance (Public, Private or none), Ethnicity, Race, or living with one biological parent, two biological parents, a stepparent, a relative, or other.

SA2: Examine the effectiveness of CIS-telehealth relative to inpatient and in-person OCIC among children with similar CHRT scores.
	
 Our working hypothesis is that CIS-telehealth will be associated with poorer reduction in emotional arousal and perceived stress levels in response to COVID-19 the pandemic relative to CIS-inpatient and CIS-in-person.

SA3: Assess patient and parent treatment satisfaction with CIS-telehealth relative to inpatient and in-person OCIC among children with similar CHRT scores.
	
 Our working hypothesis is that CIS-telehealth is associated with less patient satisfaction than inpatient and in-person OCIC among children with similar CHRT scores.

Exploratory Aim
	

[figure not shown]
Specific Aims	Hypothesis

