9.1. Sample Size Determination

We proposed to recruit approximately 244 eligible cases that will be followed in three treatment arms: telehealth CIS, in-person OCIC, and inpatient. We expect that the sample sizes for the three arms will be *at least* 75, 75, and 70 respectively. These numbers account for an expected 10 % dropout rate; 220 participants are expected to complete study procedures. Prior evidence suggests that the 6-month inpatient readmission rate for adolescents with a prior history of suicidality is approximately 19%.¹⁰⁸ Preliminary data suggest that almost 10% of adolescents who received OCIC treatment following a suicidal event could have recurrent suicidal attempts during the following 6 months after OCIC treatment (preliminary unpublished data from the sites from Dallas and Cincinnati). Therefore, if we assume the hazard ratio (inpatient group vs. OCIC group) will be approximately 2.8 and the readmission rates over 6 months for the two groups will be 19% (for the inpatient group) vs. 10% (for the OCIC group), we will be able to achieve the statistical power at 0.70 given the two-side alpha value = 0.05. We expect numbers for the

Telehealth CIS to be larger than the inpatient group. We will achieve similar power when we compare the Telehealth CIS group with the inpatient group. The power is likely lower than 0.6 when we compare Telehealth CIS with the OCIC group since the effect size (i.e., hazard ratio < 2). The power calculation, based on the assumption that 19% (inpatient group) vs. 10% (Telehealth CIS or OCIC group) will be the averaged recurrence rates for the two arms across the four sites, was performed using the powerSurvEpi package in the software R. For continuous outcomes, we expect that the two-group comparison can achieve the power at 0.84 when the effect size Cohen's d is 0.5 and sample sizes for the first and second group are 75 and 70, respectively. Alternatively, we will achieve the power at 0.76 if we use ANOVA to evaluate whether the continuous outcome differs among the three groups given the effect size $f^2 = 0.2$

For purposes of analysis, the following populations are defined:

Population	Description
Enrolled	All participants who sign the ICF
Observational	All patients will be followed in three treatment arms (telehealth CIS, in-person OCIC, and inpatient)

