increased risk of serious suicide attempts and suicide.⁶¹⁻⁶³ The cultural context of adolescent suicidal behavior and help-seeking is important and differs among races and ethnic groups.¹⁰⁵ For example, in the Hispanic community, families are much less likely to seek mental health professionals in help seeking and prefer to rely on family first.⁶⁴ Ethnic groups and races differ in rates of adolescent suicidal behaviors.^{105, 106} However, the gap has been decreasing between white adolescent suicides and African American suicides due to an increase in male African American deaths by suicide.⁶⁵⁻⁶⁷ Living situation (living with one biological parent, two biological parents, a stepparent, a relative, or other) is an important HTE for adolescents because living with one parent or the presence of a stepparent was correlated with an increased risk of suicidal thoughts and suicide attempts by adolescents.^{68, 69}

The analysis plan:

To test Aim 1, we will use Cox proportional regression model (CPR) to test whether the telehealth only CIS; outpatient, in-person CIS; and in-patient CIS groups have different incidence rates for recurrent episodes within 3 months. We expect that the sample sizes for the three arms will be *at least* 75, 75, and 70 respectively. To evaluate Aims 2 and 3, we will use the generalized linear model (GLM) to evaluate whether telehealth only CIS; outpatient, in-person CIS; and in-patient CIS groups have different levels of changes in emotional arousal (Aim 2) and treatment satisfaction (Aim 3) at 3 months, after adjusting for several covariates (e.g., age, gender, triage “location”). For CPR, we will have power for our pilot study greater than 0.70 assuming a hazard ratio of 2.8 and greater than 0.8 for our GLM analyses assuming $f^2 = 0.1$ and correcting for multiple comparisons.

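### The Aim 1 Cox test is worded for 3 months, but its stated power of 0.70 comes from 6-month rates, and the plan does not fix one primary window

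*Combined protocol and SAP*

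**What the plan says.** Sections 4.2 and 9.2.3 (under the analysis plan) carry the same paragraph. The Aim 1 Cox model is to test whether the three groups "have different incidence rates for recurrent episodes within 3 months", and the paragraph goes on to claim "power for our pilot study greater than 0.70 assuming a hazard ratio of 2.8".

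Section 9.1 is the only place where that power is derived. It assumes that "the hazard ratio (inpatient group vs. OCIC group) will be approximately 2.8" and that "the readmission rates over 6 months for the two groups will be 19% (for the inpatient group) vs. 10% (for the OCIC group". It concludes that "we will be able to achieve the statistical power at 0.70 given the two-side alpha value = 0.05". Arm sizes are at least 75 (telehealth), 75 (OCIC) and 70 (inpatient), already net of 10% dropout. The same 19% and 10% are applied to telehealth against inpatient. No 3-month rate enters any power calculation.

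The other places that bear on the window do not settle it:
- Section 9.2.1, primary row: a Cox model for time to first suicidal event, with no window stated.
- Section 3, SA1: response is a delay in first recurrence and "a lower number of suicidal events over 90 days and 180 days".
- Sections 4.1 and 8.2.1: surveys every two weeks for 6 months, and adverse events collected to 180 days.

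**The concern.** The power of a Cox comparison depends on the number of events. A figure built on 6 months of events cannot be carried over to a 3-month test unless nearly all events come early, and the plan does not argue that they do. As written, the power stated beside the 3-month test belongs to a different horizon.

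The plan also leaves the window open: 3 months in two sections, none in the primary-endpoint row, both 90 and 180 days in SA1. In an observational study where treatment is known, this allows the window to be chosen after outcomes have accrued. Aim 1 is the primary safety question in suicidal adolescents, and a null result from a test with far fewer events than implied could be read as reassurance about telehealth.

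**Working it through.** **Inputs.** From 9.1: inpatient 70, OCIC 75 (telehealth is also 75, so the same figures apply to telehealth vs inpatient at the same rates); 6-month rates 19% and 10%; hazard ratio (HR) 2.8; two-sided 0.05. Section 9.1 names the powerSurvEpi package but not the function, so two standard formulas are used, with D the expected number of events:
- Freedman-type: power = Φ(√(kD)·|HR−1|/(k·HR+1) − 1.96), with k = 70/75.
- Schoenfeld: power = Φ(√(D·p(1−p))·ln HR − 1.96), with p = 70/145.

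**Step 1: the plan's own figure, 6 months.** D = 70×0.19 + 75×0.10 = 13.3 + 7.5 = 20.8.
- Freedman: 4.406×1.8/3.613 − 1.96 = 0.235, power 0.59.
- Schoenfeld: 2.279×1.030 − 1.96 = 0.387, power 0.65.

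So 0.70 is not reproduced. It needs about 24 events (Schoenfeld) or 27 (Freedman). Three departures from the stated inputs do reach about 0.70: one-sided alpha (Freedman 0.71); enrolled rather than completer numbers (Schoenfeld 0.70); or raising the inpatient rate to about 25.5%, which is what HR 2.8 on a 10% OCIC rate implies (simulated log-rank 0.70).

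**Step 2: the 3-month window.** The documents give no 3-month rates for this purpose, so the share of 6-month events falling by month 3 is an assumption:
- Constant hazard: 1−√0.81 = 10.0% and 1−√0.90 = 5.1%, so D = 7.00 + 3.85 = 10.85, or 52% of 20.8.
- About 60%: section 2.2 reports a 6% psychiatric ED return within 90 days of the first OCIC visit, set against the assumed 10% at 6 months. The endpoint differs.
- 70%: section 2.2 says almost half of OCIC reattempts came in the first month after discharge. With the rest spread evenly over months 2 to 6, 0.5 + 0.5×(2/5) = 0.70.

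| Share of 6-month events | D | Freedman | Schoenfeld |
|---|---|---|---|
| 52% | 10.85 | 0.35 | 0.40 |
| 60% | 12.5 | 0.40 | 0.44 |
| 70% | 14.6 | 0.45 | 0.50 |
| 100% (upper limit) | 20.8 | 0.59 | 0.65 |

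The three departures that reach 0.70 at 6 months give between 0.42 and 0.59 at 3 months, over shares from constant hazard to 70%.

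**Step 3: the hazard ratio.** Rates of 19% and 10% imply HR = ln(0.81)/ln(0.90) = 2.0, not 2.8. At HR 2.0 the power is 0.34 to 0.35 at 6 months and 0.20 to 0.26 at 3 months. This is a separate defect from the window, but any restated power has to deal with it.

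**Step 4: the actual endpoint.** The 19% and 10% are readmission and attempt rates. The primary endpoint in section 2.2 is a wider composite that includes emergency or urgent evaluations. Section 2.2 reports suicidal events in 27.3% of Dallas OCIC respondents at 6 months. Taking that as the OCIC rate, with 50% to 70% of the 6-month cumulative hazard by month 3:
- HR 2.8: about 36 to 47 events, power 0.83 to 0.94.
- HR 2.0: about 30 to 40 events, power 0.46 to 0.59.

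**The case against.** Several points on the other side have force.

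- *The primary analysis is not fixed at 3 months.* A reader might infer that the plan commits to a 3-month cut and throws away half the follow-up. The documents do not support that: 9.2.1, which specifies the primary analysis, has no cut, and in SA1 the 90 and 180 days attach most directly to the number of events. The defect is an inconsistent window.
- *A 3-month test might still be well powered.* A reader might infer that 0.70 is out of reach at 3 months. That holds only on the 19% and 10% inputs. With the composite rate and HR 2.8 together, power would exceed 0.80. The plan does not make that calculation, and at HR 2.0 it would not hold.
- *Ninety days has a case.* Treatment is short, section 2.2 places the greatest reattempt risk in the first month after inpatient discharge, and the study lasts 12 months with enrolment to month 10. If follow-up stopped at month 12 and enrolment were even from month 2 to month 10 (assumptions), (6−2)/8 = 50% of participants would reach 6 months and (9−2)/8 = 88% would reach 3 months. The 20.8 events would then be optimistic. However, 4.3 also allows the study to run to the last visit, and censoring means that using all follow-up never yields fewer first events than a 90-day cut.
- *A statistical analysis plan is promised, and this is called a pilot.* Section 9.2 promises the plan before database lock but does not list the window among what it will settle, and lock comes after outcomes have accrued. The pilot label, and the admission in 9.1 that telehealth vs OCIC is likely below 0.6, temper the consequences but do not correct the 0.70.

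**Conclusion.** The concern stands in this form: the plan does not fix one primary window, and the power above 0.70 stated with the 3-month test is not supported for it. On the plan's rates, arm sizes and HR 2.8, power is 0.59 to 0.65 at 6 months and about 0.35 to 0.50 at 3 months. The 3-month range rests on 52% to 70% of events occurring by month 3. That is an assumption range, not a finding. The conclusion does not depend on it, because even with all 20.8 events by month 3 the power would be at most 0.65.

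A reader might also infer that switching to 180 days restores 0.70. It does not: 6-month power already falls short on the literal inputs, and more so at the hazard ratio of 2.0 that those rates imply.

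**What to change.** State one primary window for time to first suicidal event, in the same words in 4.2, 9.2.1 and 9.2.3, before outcomes are examined. A window of 180 days with censoring uses all collected events, with 90 days as a secondary analysis. If the sponsor prefers 90 days as primary, the protocol should justify it.

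Then restate the power in 4.2, 9.1 and 9.2.3 using event rates for that same window and for the composite endpoint as defined, with a hazard ratio that follows from those rates. Name the function used and whether the numbers are enrolled or completing participants. If 180 days is chosen, say how many participants are expected to be followed that long.

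The cost is changed wording and a stated power that will probably be less favourable. No new data, visits or participants are needed.

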
 Evaluate the safety of CIS-telehealth relative to inpatient and OCIC-in-person among children with similar CHRT scores. 	
 Time to first recurrence of a suicidal event Number of suicidal events Severity of suicidal ideation
Secondary	

 Examine the effectiveness of CIS-telehealth relative to inpatient and in-person OCIC among children with similar CHRT scores. 	
 Score from PROMIS Short Form v 1.0-General Life Satisfaction-Short Form 5a (to assess the parent's well-being) Score from PROMIS Parent-Proxy Life Satisfaction-Short Form 8a Score from PROMIS Pediatric Life Satisfaction-Short Form 4a Score from CHRT-SR at baseline and follow-up visits

 Assess patient and parent treatment satisfaction with CIS-telehealth relative to inpatient and in-person OCIC among children with similar CHRT scores. 	
 Score from Client Satisfaction Questionnaire (CSQ-8)
Tertiary/Exploratory	

 Does Telehealth CIS lead to greater reduction of emotional arousal or perceived stress levels in response to COVID-19 the pandemic 	
 Scores from the COVID-19 survey

CONFIDENTIAL

Overall Design: Observational Design

Number of Participants: CCHMC- 61; other 3 sites- 61 each; total- 244 from all 4 sites

Treatment Groups: Inpatient Psychiatric Treatment vs. Outpatient Crisis Intervention Clinic (OCIC) vs. Telehealth Crisis Intervention Services (CIS)

Duration: 12 Months (1 Years)

2. Introduction

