- All screening evaluations must be completed and reviewed to confirm that potential participants meet all eligibility criteria. The investigator will maintain a screening log to record details of all participants screened and to confirm eligibility or record reasons for screening failure, as applicable.
- Time to first recurrence of a suicidal event and number of suicidal events will be measured with the Suicidal Event Form for START (appendix), a short supplemental form (developed by our team), at baseline and every two weeks (see Schedule of Events; appendix)
- Severity of suicidal ideation will be measured with the self-report scale: CHRT-SR (appendix) at baseline and every two weeks (see Schedule of Events; appendix).
- The Suicidal Treatment AlteRnatives for Teens (START)-Clinical Features (CF) form (appendix), a short supplemental form with 13 questions (developed by our team), will be completed at baseline (within 72 hours of admission to inpatient or OCIC) and every two weeks to monitor substance use based on information from patient, parent, and/or EHR.
- The C-SSRS Self-Report form, included in the CF survey, will be completed at baseline and every 2 weeks by the participant to assess for suicidal thoughts and behaviors.
- Satisfaction with Life (SL) will be measured with self-report scales including the PROMIS Short Form v 1.0-General Life Satisfaction-Short Form 5a (to assess the parent's well-being), PROMIS Parent-Proxy Life Satisfaction-Short Form 8a, and PROMIS Pediatric Life Satisfaction-Short Form 4a every 2 weeks.
- Treatment satisfaction (TS) data about, telehealth CIS, OCIC and inpatient psychiatry will be collected only after two weeks and/or subsequent to completion of inpatient psychiatry or OCIC. TS will be measured once with the Client Satisfaction Questionnaire (CSQ-8) 95 after completion of telehealth, OCIC or inpatient treatment which is typically completed by week 3 (but could be completed by week 2 to week 6).
- COVID-19 Impact survey will be completed at week 2 and will gather information regarding the impact of the pandemic on the participant and families social, emotional, and economic functioning.

- The Self-Assessment Manikin (SAM) questionnaire will be completed at baseline and week 12 follow up survey.

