9.2.1. Efficacy Analyses

Endpoint	Statistical Analysis Methods
Primary	The primary outcome measure for this proposed research will be the time to first recurrence of a suicidal event. We will examine if the treatment option can predict the “time to the first suicidal event” using the Cox-proportional hazard model.
Secondary	The secondary outcome is Satisfaction with Life (SL), which will be measured every two weeks. The treatment effect on such time-series

	data will then be analyzed using mixed-effect ordinary logistic regression model.
Exploratory	Will be described in the statistical analysis plan finalized before database lock

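### Aim 2 (effectiveness) has conflicting endpoints: the analysis plan tests emotional arousal, the objectives table lists PROMIS and CHRT-SR, and CHRT-SR gets no final between-arm analysis

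*Combined protocol and SAP*

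**What the plan says.** The synopsis lists a secondary objective, "Examine the effectiveness of CIS-telehealth relative to inpatient and in-person OCIC among children with similar CHRT scores". Its endpoints are three PROMIS life-satisfaction scores and "Score from CHRT-SR at baseline and follow-up visits". Arousal and stress sit lower, in the tertiary/exploratory row: "Does Telehealth CIS lead to greater reduction of emotional arousal or perceived stress levels". The only endpoint given there is the COVID-19 survey score.

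Section 3 keeps the effectiveness wording for SA2 but attaches a different hypothesis: "CIS-telehealth will be associated with poorer reduction in emotional arousal and perceived stress levels". It names neither PROMIS nor CHRT-SR. Sections 4.2 and 9.2.3 then give Aim 2 its test, a generalized linear model of whether the arms "have different levels of changes in emotional arousal (Aim 2) and treatment satisfaction (Aim 3) at 3 months", with power put above 0.8.

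Section 9.2.1 sets out a Cox model for time to first suicidal event and one secondary analysis: "The secondary outcome is Satisfaction with Life (SL), which will be measured every two weeks". CHRT-SR does not appear there. In section 9.2.3 it appears by name only under the interim analysis at the end of month 6.

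On timing, sections 4.1 and 8 and the Schedule of Events give the COVID-19 survey once, at week 2. Section 8 adds: "The Self-Assessment Manikin (SAM) questionnaire will be completed at baseline and week 12 follow up survey".

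**The concern.** The same objective carries different outcomes depending on where one reads. An outcome that the objectives table calls exploratory gets the Aim 2 test and its power statement. CHRT-SR, which the table lists as a secondary endpoint, gets no final comparison.

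CHRT-SR also has a second role. The synopsis lists severity of suicidal ideation under its first (safety) objective. Section 8 measures it with CHRT-SR, and section 8.1 with CHRT-SR and the C-SSRS. Section 9 has no outcome model for ideation severity either; it appears only as a heterogeneity factor in section 9.2.3.

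At stake is whether the Aim 2 result answers the question it is labelled with. The Aim 2 test could be run and reported exactly as specified without any final between-arm comparison of a suicidal-ideation score. With several outcome definitions in force, a reader of the report could not tell which one was planned.

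**Working it through.** **The plan's own figure first.** Section 9.2.3 claims power above 0.8 for the GLM at f² = 0.1, corrected for multiple comparisons. Inputs: arms of 75, 75 and 70 give N = 220, and three arms give 2 numerator df. Assumptions: three covariates, so 220 − 3 − 3 = 214 denominator df; two-sided alpha 0.05, which section 9.1 states only for the Cox calculation; Bonferroni divisors of 3 or 6, because the number of comparisons is not stated.

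- Noncentrality λ = f² × N = 0.1 × 220 = 22.
- Power from the noncentral F: 0.991 at alpha 0.05, 0.973 at 0.05/3 = 0.0167, 0.953 at 0.05/6 = 0.0083.
- One pair of arms, N = 75 + 70 = 145, λ = 14.5, 1 df: 0.966 at 0.05 and 0.915 at 0.0167.

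The claim is met in every variant. The calculation uses no property of the outcome, so it would read the same for CHRT-SR, PROMIS or arousal. Power does not settle which endpoint was meant.

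**Endpoints side by side.**

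| Place | Outcome given for effectiveness / Aim 2 |
|---|---|
| Synopsis, secondary objective | Three PROMIS scores, CHRT-SR |
| Section 2.2 (text following the adult recommendations) | Time to first event, number of events, treatment satisfaction, life satisfaction |
| Section 3, SA2 | Emotional arousal, perceived stress |
| Sections 4.2 and 9.2.3 | Change in emotional arousal at 3 months |
| Section 9.2.1 (names the secondary outcome) | Satisfaction with Life |

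**Instrument, schedule and final between-arm model.**

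| Instrument | Time points | Final model |
|---|---|---|
| PROMIS (three forms) | 12 (baseline to week 22) | Yes, section 9.2.1 |
| CHRT-SR | 12 (baseline to week 22) | None |
| SAM | 2 (baseline, week 12) | Not named in any |
| COVID-19 survey | 1 (week 2) | Section 9.2.3, as covariates and in its own predictor analysis |

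**Can the interim stand in for a final CHRT-SR analysis?** Section 4.2 projects enrolment from month 2 to month 10. Reading the interim as the end of project month 6, nobody enrolled in months 7 to 10 is in it. The earliest participant has at most 6 − 1 = 5 months of the planned 6 months of follow-up. Its stated purpose is a decision about revising the protocol and continuing a treatment group, with a threshold of d > 1.2. It is not an estimate of effectiveness. The four scores listed for the interim are the same four that the objectives table gives for effectiveness.

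**Can the COVID-19 survey show a reduction?** A change from baseline to follow-up needs at least two measurements, and the survey supplies one. The SAM timing fits a 3-month change, but no text connects the SAM to arousal, to Aim 2 or to any model. No repeated instrument is named for perceived stress.

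**A further overlap.** The COVID-19 survey plan in section 9.2.3 makes changes in perceived stress covariates in the Aims 1–3 comparisons, while SA2 makes reduction in perceived stress an Aim 2 outcome. The same quantity cannot usefully be both in one analysis.

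**The case against.** The strongest reply is that the plan does analyse what matters. Section 9.2.1 gives final models for suicidal events and for life satisfaction, and section 2.2 describes effectiveness largely in those terms. This stands. It narrows the analysis gap to CHRT-SR and the ideation severity that it measures.

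Second, section 9.2 promises a statistical analysis plan before database lock, and the work is a self-described pilot. This lowers the urgency but does not cure the conflict. Section 9.2 describes that plan as covering participant selection and the handling of missing, unused and spurious data. Sections 9.2.1 and 9.2.2 defer only exploratory analyses to it. Section 9.2.3 already specifies the Aim 2 test.

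Some stronger readings are tempting but are not supported:

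- A reader might infer that the effectiveness conclusion rests on a momentary arousal rating alone. The documents never say what the SAM measures, and events and life satisfaction have final models.
- A reader might infer that no change of any kind can come from the COVID-19 survey. Its items are not shown, and section 9.2.3 speaks of changes in levels during the pandemic, so retrospective change items are possible.
- A reader might count the candidate endpoints and compute a false-positive rate. That needs independent endpoints and free selection after the data are seen. Three of the candidates are life-satisfaction scores, section 9.2.3 mentions correction for multiple comparisons, and the analysis plan is to be final before lock.
- A reader might conclude that CHRT-SR must rank above PROMIS. The objectives table does not rank the four scores.

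**Conclusion.** The point holds as a conflict of endpoints with one missing analysis. Aim 2 is tested on an outcome that the objectives table ranks as exploratory. One of the four listed effectiveness endpoints, CHRT-SR, has no final between-arm analysis despite 12 scheduled measurements. The arousal and stress objective is tied to an instrument with one time point and no baseline, while the SAM, with two, is attached to nothing.

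It should be fixed, but it does not threaten the study. The primary endpoint and its Cox model are unaffected, PROMIS has a final model, and the GLM power claim reproduces whichever outcome is meant. The conclusion assumes that the text supplied is the whole current plan. A separate analysis plan that names a final CHRT-SR model would close that part, though the sections would still need to agree.

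**What to change.** 1. Align the synopsis table, section 3 (SA2), section 4.2, section 9.2.1 and section 9.2.3 on one Aim 2 endpoint set. Following the objectives table, that set is the three PROMIS scores and CHRT-SR.
2. Add a final between-arm CHRT-SR analysis adjusted for baseline CHRT-SR, for example at week 12 or as a mixed model over the scheduled visits. Baseline adjustment also suits an objective framed around children with similar CHRT scores. State whether the same analysis serves ideation severity under the first objective.
3. Keep change in emotional arousal exploratory and name its instrument and time points: the SAM at baseline and week 12, if the sponsor confirms that this is the intended measure.
4. Restate perceived stress as a comparison of week-2 levels, unless the survey contains retrospective change items. If it does, say so and name them.
5. Do not use change in perceived stress as a covariate in Aim 2 where it is also an outcome.

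The cost is wording and one added model. Every instrument is already scheduled. The small downside is that arousal is no longer the headline Aim 2 result.
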